6.1 Blinatumomab Infusion interruption/dose modification due to adverse events

Dose modifications (interruptions, withholdings, and criteria for restarting treatment) are summarized in table 2.

Table 2. Dose interruptions, modifications and criteria for discontinuation and recommencement of therapy

Toxicity	Grade	Action
Cytokine Release Syndrome (CRS) +/- DIC/coagulopathy	Grade 2	Continue blinatumomab. Give IV fluid bolus (500-1000mL normal saline); repeat as necessary to keep systolic BP >90mmHg. If systolic BP ≤90mmHg after 2L IV normal saline, withhold blinatumomab and consider ICU transfer and inotropic support. Manage blinatumomab re-commencement as per grade 3 AE, below.
	Grade 3	Withhold blinatumomab until resolved to < or = grade 1, then restart blinatumomab at the next lowest dose* after dexamethasone pre-medication (see table 1). Re-escalate to the next highest dose level after 7 days and to the highest dose level after a further 7 days if toxicity does not recur.
	Grade 4	Discontinue blinatumomab permanently.
Neurological Toxicity	Seizure	Discontinue blinatumomab permanently if more than one seizure occurs.
	Grade 3*	Withhold blinatumomab for at least 3 days and until no more than Grade 1 (mild) and, then restart blinatumomab at the next lowest dose level†, after dexamethasone pre-medication. Re-escalate to the next highest level after 7 days and to the highest dose level after a further 7 days if the toxicity does not recur. If the toxicity occurred at 9 mcg/day, or if the toxicity takes more than 7 days to resolve, discontinue blinatumomab permanently.
	Grade 4	Discontinue blinatumomab permanently.
Other Clinically Relevant Adverse Reactions at least possibly related to blinatumomab	Grade 3	Withhold blinatumomab until no more than Grade 1 (mild) toxicity, then restart blinatumomab at the next lowest dose level†, after dexamethasone pre-medication. Re-escalate to the next highest level after 7 days and to the highest dose level after a further 7 days if the toxicity does not recur. If the

		toxicity occurred at 9 mcg/day If the toxicity takes more than 14 days to resolve, discontinue blinatumomab permanently.
	Grade 4	Discontinue blinatumomab permanently.
Unrelated AEs	All grades	If blinatumomab was interrupted due to an AE that was ultimately deemed by the investigator to be unrelated to blinatumomab (eg. Infection resulting in febrile neutropenia), blinatumomab can be resumed at the same dose as prior to dose interruption, when the patient is deemed by the investigator to be clinically stable. Pre-medication with dexamethasone as per Table 1 should be given prior-to and after recommencement of blinatumomab.

* **NB.** Grade 3 neurotoxicity due to >1 generalized seizure will mandate permanent cessation of blinatumomab. †The next lowest dose is 28mcg/day if the toxicity occurred at 112mcg/day or 9mcg/day if the toxicity occurred at 28mcg/day. If the toxicity occurred at 9mcg/day, re-challenge after resolution to grade 1 or less may be attempted after appropriate pre-medication. Dose modifications other than those described in the table may be made, if deemed, after discussion with the PI, to be in the patient's best interests.

Common Terminology Criteria for Adverse Events (CTCAE) clinical grade 4 adverse events (AEs) that are characteristic of blinatumomab (i.e. CNS events and cytokine release syndrome (CRS), described in more detail below), will require permanent discontinuation of blinatumomab. For all other grade 4 AEs, the Principal Investigator or designee should be notified; an assessment should be made to determine causality and the risk:benefit for each individual patient to continue or discontinue blinatumomab treatment. CTCAE version 5.0 will be used for grading of AEs, with the exception of CRS (graded according to appendix C) and neurotoxicity (graded according to appendix E). Please see Appendix F for the CTCAE grading of common organ-associated AEs.

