6.1.1 Infusion interruption/dose modification due to CNS events

Please see Appendix E for the grading of CNS-related AEs. In case of CNS-related AEs, dexamethasone should be administered at a dose of at least 24 mg/day. The dexamethasone dose

will then be reduced step-wise over approximately 4 days. The following investigations should be performed:

If the CNS-related adverse event is CTCAE grade 3 or higher, blinatumomab will be stopped immediately and a physical exam, vital signs and safety laboratory tests will be performed. Additional measures can be taken at the discretion of the investigator, depending on the nature of the adverse event. The following diagnostic investigations are recommended:

1. A non-contrast CT scan of the head to exclude CNS hemorrhage.
2. Assessment of cerebrospinal fluid should be performed for cytology, cell count, B- and T-cell measurement (by flow cytometry), and viral studies (HSV 1/2, HSV6, JC virus and adenovirus).
3. Additional investigations of the CSF should be performed as clinically appropriate.
4. A contrast-enhanced magnetic resonance imaging (MRI) of the head should be performed for subjects who had to interrupt treatment because of a CNS event grade 3, before treatment is resumed.

Please note that there may be circumstances in which some of the above investigations will not be able to be performed (for example, CSF assessment may not be possible in patients with low platelet counts or abnormal coagulation parameters, for safety reasons, and MRI may not be possible if patients are unable to lie still for the duration required to perform this examination). Therefore, not performing these tests will not be considered protocol deviations.

For subjects who experience a CTCAE grade 3 CNS adverse event or serious adverse event leading to treatment interruption, if the event has decreased to at least CTCAE grade 1 within 1 week, treatment may be restarted within 2 weeks, but not earlier than 72 hours (3 days) after the infusion was stopped. When recommenced, treatment will begin at the next lowest dose.

However, a grade 3 CNS event leading to treatment interruption at the dose of 9 µg/day or a CNS event needing more than 1 week to resolve to grade less than or equal to 1 will result in permanent treatment discontinuation.

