In case of CNS-related events CTCAE grade 4, or in case of occurrence of more than one generalized seizure (considered grade 3 CNS toxicity), the infusion of blinatumomab will be stopped immediately and treatment will be permanently discontinued.

For patients in whom the criteria for recommencement of blinatumomab, as described above, are met, blinatumomab can be recommenced, following dexamethasone premedication as described in Table 1, at the next lowest dose. Blinatumomab will be escalated to the next highest dose after 7 days, if the toxicity does not recur. The subject should remain hospitalized until at least 2 days after re-escalation to the dose at which the toxicity first occurred.

If the CNS event was a generalized seizure (CTCAE grade 2 or above), appropriate prophylactic anticonvulsant treatment will be administered prior to recommencing therapy.

6.1.2 Dose interruption and modification for cytokine release syndrome (CRS) and/or DIC/coagulopathy

For CTCAE grade 2 CRS which requires inotropes, grade 3 CRS and CTCAE grade 3 DIC/coagulopathy, blinatumomab can then be restarted at the next lowest dose (see table 2), once the event has returned to grade ≤ 1 severity. If the event occurred at a dose of 9 mcg/day and no neurological toxicity of greater than or equal to grade 3 occurred, treatment with blinatumomab will be interrupted until the event resolves to less than or equal to grade 1 and then resumed at 9 mcg/d, after dexamethasone pre-medication as described in Table 1. However, if the AE lasts for ≥ 2 weeks, then blinatumomab will be permanently discontinued.

In CRS of \geq grade 2, dexamethasone should be administered orally or IV at an initial dose of at least 3 x 8 mg/day. The dose can then be reduced step-wise over approximately 4 days according to clinical response.

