Appendix E: ASTCT INCANS Consensus Grading for Adults

Neurotoxicity Domain	Grade 1	Grade 2	Grade 3	Grade 4
ICE score*	7-9	3-6	0-2	0 (patient is unarousable and unable to perform ICE)
Depressed level of consciousness [†]	Awakens spontaneously	Awakens to voice	Awakens only to tactile stimulus	Patient is unarousable or requires vigorous or repetitive tactile stimuli to arouse. Stupor or coma.
Seizure	N/A	N/A	Any clinical seizure, focal or generalized, that resolves rapidly or non-convulsive seizures on EEG that resolve with intervention	Life-threatening prolonged seizure (>5 min); or repetitive clinical or electrical seizures without return to baseline in between
Motor findings [‡]	N/A	N/A	N/A	Deep focal motor weakness such as hemiparesis or paraparesis
Elevated ICP/cerebral edema	N/A	N/A	Focal/local edema on neuroimaging [§]	Diffuse cerebral edema on neuroimaging; decerebrate or decorticate posturing; or cranial nerve VI palsy; or papilledema; or Cushing's triad

ICANS grade is determined by the most severe event (ICE score, level of consciousness, seizure, motor findings, raised ICP/cerebral edema) not attributable to any other cause; for example, a patient with an ICE score of 3 who has a generalized seizure is classified as grade 3 ICANS.

N/A indicates not applicable.

*A patient with an ICE score of 0 may be classified as grade 3 ICANS if awake with global aphasia, but a patient with an ICE score of 0 may be classified as grade 4 ICANS if unarousable.

† Depressed level of consciousness should be attributable to no other cause (eg, no sedating medication).

‡ Tremors and myoclonus associated with immune effector cell therapies may be graded according to CTCAE v5.0, but they do not influence ICANS grading.

§ Intracranial hemorrhage with or without associated edema is not considered a neurotoxicity feature and is excluded from ICANS grading. It may be graded according to CTCAE v5.0.

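### Table 2 conflicts with itself and with 6.1.1 on grade 3 neurotoxicity: re-challenge at 9 mcg/day (footnote †), and permanent stopping after repeat non-generalized seizures

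*Combined protocol and SAP*

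**What the plan says.** **Toxicity at 9 mcg/day.** The grade 3 neurological row of Table 2 begins "Withhold blinatumomab for at least 3 days and until no more than Grade 1 (mild) and, then restart blinatumomab at the next lowest dose". It ends by stopping blinatumomab for good if the event arose at 9 mcg/day or took more than 7 days to resolve. Section 6.1.1 gives the same two grounds for a permanent stop. Footnote †, which hangs on that row's next-lowest-dose wording, adds: "If the toxicity occurred at 9mcg/day, re-challenge after resolution to grade 1 or less may be attempted after appropriate pre-medication".

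**Repeat seizures.** The seizure row of Table 2 reads "Discontinue blinatumomab permanently if more than one seizure occurs" and does not limit the seizure type. Footnote *, attached to the grade 3 row, reads "Grade 3 neurotoxicity due to >1 generalized seizure will mandate permanent cessation of blinatumomab". Section 6.1.1 likewise mandates the stop "in case of occurrence of more than one generalized seizure (considered grade 3 CNS toxicity"). Section 6.1 sends the grading of neurotoxicity to Appendix E, where grade 3 includes "Any clinical seizure, focal or generalized, that resolves rapidly or non-convulsive seizures on EEG that resolve with intervention".

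**Hospital stay after a CNS restart.** Section 6.1.1 sets a minimum: two days after the patient is back at the dose where the toxicity first appeared. Section 6.1.4 keeps the patient in hospital through re-escalation and for three days at the top dose of that cycle.

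**The concern.** Ward staff apply these rules during an acute event. In each of the two Table 2 situations, one line tells them to end blinatumomab and another lets them give it again. A patient with grade 3 neurotoxicity in the first week, at the lowest dose, could be re-exposed on the strength of a footnote when the row above it forbids this. A patient with two focal seizures could be stopped or restarted depending on which row is read.

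The statistical consequence is small. Under the toxicity definition in section 14.0, a grade 3 neurological event that resolves within a week counts if it recurs at grade 3 or higher on re-challenge. Which instruction is followed therefore decides whether that limb can apply to the patient at all. The event may still count under the nivolumab immune-related limb in either case.

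**Working it through.** The documents give no figure to reproduce here. The check sets the rules side by side and counts infusion days.

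**1. Grade 3 neurotoxicity at 9 mcg/day**

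| Place | Instruction |
|---|---|
| Table 2, grade 3 neurological row | Stop permanently |
| 6.1.1 | Stop permanently |
| Table 2, footnote † | Re-challenge may be tried once at grade 1 or less |
| 6.1.2 (CRS at 9 mcg/day) | Resume at 9, but only if there was no grade 3 or higher neurotoxicity |

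The footnote is the odd one out. The exclusion in 6.1.2 shows that the plan separates neurotoxicity from CRS at this dose. Section 4.3 plans 9 mcg/day for the first 7 infusion days of cycle 1 only. The two courses total 28 + 28 = 56 infusion days, so the conflict concerns 7/56 = 12.5% of them. They come early, and 5.1.3 says that neurologic events are most frequent in the first few days and at dose escalation. A later return to 9 mcg/day after a step-down adds nothing, because 6.1.4 ends treatment on any related grade 3 or higher recurrence after a restart.

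**2. More than one seizure**

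| Situation | Outcome | Conflict? |
|---|---|---|
| More than one generalized seizure | Seizure row, footnote * and 6.1.1 all stop | No |
| Repetitive seizures without return to baseline, or longer than 5 minutes | Grade 4 in Appendix E: stop | No |
| Related grade 3 seizure after a restart | 6.1.4: stop | No |
| Not resolved within 7 days | Grade 3 row and 6.1.1: stop | No |
| At 9 mcg/day | Row and 6.1.1: stop (subject to part 1) | No, once † is corrected |
| Two or more focal or non-convulsive grade 3 seizures, recovery between them, before any restart, at 28 or 112, resolved within 7 days | Seizure row: stop. Grade 3 row: withhold, then restart lower | **Yes** |

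In the last case the infusion is normally already off, since 6.1.1 says: "If the CNS-related adverse event is CTCAE grade 3 or higher, blinatumomab will be stopped immediately".

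**3. Hospital stay**

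Inputs: doses of 9, 28 and 112 mcg/day with 7-day steps, and at most 28 infusion days per cycle. If infusion is interrupted on infusion day k, 28 − k days remain (numbering rule in 6.1.4). Stays are counted in days from restart and capped at 28 − k.

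- Event at 28: restart at 9, back to 28 at day 7, up to 112 at day 14. 6.1.1 gives 7 + 2 = 9. 6.1.4 gives 14 + 3 = 17.
- Event at 112: restart at 28, back to 112 at day 7. 6.1.1 gives 7 + 2 = 9. 6.1.4 gives 7 + 3 = 10.

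| Event | k | 6.1.1 | 6.1.4 |
|---|---|---|---|
| At 28, cycle 1 | 8–11 | 9 | 17 |
| | 12 | 9 | 16 |
| | 13 | 9 | 15 |
| | 14 (112 not reached) | 9 | 7 + 3 = 10 |
| At 112 | up to 18 | 9 | 10 |
| | 19 | 9 | 9 |
| | 20 | 8 | 8 |
| | 21, 22, 23, 24 | 112 not regained; 7, 6, 5, 4 days to cycle end | 3 |
| | 25–28 | to cycle end | to cycle end |

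There are 56 − 7 = 49 event days at 28 or 112. 6.1.4 is longer by 6–8 days on 6 of them and by 1 day on 23. The two are equal on 12, and 6.1.4 is shorter by 1–4 days on 8 (6 + 23 + 12 + 8 = 49). With both rules in force the longer stay applies. That is 6.1.4, or a tie, on 41 of the 49 days.

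**The case against.** **Table 2 is a summary, and restarting is optional.** Section 6.1 presents the table as a summary, and 6.1.1 says only that "treatment may be restarted within 2 weeks, but not earlier than 72 hours (3 days) after the infusion was stopped". Section 6.1.4 also makes resumption an option. On that reading the grade 3 row says how to restart, not that every patient must. This stands in part: a reader might infer that stopping after two focal seizures breaches 6.1.1 or footnote *, and it breaches neither. The two Table 2 rows still give opposite directions, and the limit to generalized seizures in two places would be redundant if the seizure row always prevailed.

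**The seizure row is the more specific rule.** That is plausible, but the protocol states no precedence.

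**Footnote † mainly defines the next lowest dose and is shared with the row for other adverse reactions.** That is true, and it is why the footnote should be limited rather than deleted. As attached, it still contradicts the neurological row.

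**The investigator can decide.** The footnotes allow other modifications after discussion with the principal investigator, and 6.0 requires discussion of any permanent stop. That settles a single case but does not say which default is being departed from.

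**Hospital stay.** A reader might infer that 6.1.1 and 6.1.4 contradict each other, and that a patient with an event at 28 mcg/day could go home 14 − 9 = 5 days before the step to 112. The documents do not support this. The 6.1.1 period is a minimum, and 6.1.4 expressly covers grade 3 neurological restarts and requires escalations in hospital. Section 5.1.3 allows the planned discharge only if no significant event required interruption or dose reduction, and 5.1.7 makes outpatient infusion depend on those criteria.

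**Conclusion.** The point holds as a minor inconsistency in operative safety wording. It is clearest for footnote †, where the row, 6.1.1 and the CRS rule in 6.1.2 all show what was intended. The seizure conflict is real but narrow, and the documents do not show which rule was meant. Hospital stay is not a conflict under full re-escalation. The only gap is that 6.1.1 has no reachable endpoint when the dose of first toxicity is not regained.

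No frequency can be given. Section 5.1.3 reports reversible grade 3 neurotoxicity in 6 of 21 patients with DLBCL, but no split by dose or seizure type. Sample size, stopping boundaries and operating characteristics are unaffected.

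The conclusion assumes that Appendix E governs the grading, as 6.1 states (6.1.1 also points to it, but then labels grades as CTCAE). It also assumes that the footnote markers are attached as they stand in Table 2.

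**What to change.** 1. **Footnote †:** state that re-challenge after toxicity at 9 mcg/day does not apply to grade 3 neurotoxicity. Leave it in place for other events. There is no cost beyond the edit.
2. **Seizures:** use one wording in the seizure row, footnote * and 6.1.1. As a safety default, take the stricter rule already in the seizure row (permanent stop after more than one seizure of any type), unless the sponsor justifies limiting it to generalized seizures. The cost is rare additional permanent stops.
3. **Hospital stay (optional):** do not replace the 6.1.1 minimum with a cross-reference to 6.1.4. That would add no inpatient days, and it would shorten the stay for events at 112 mcg/day on infusion days 21–24 and where a reduced dose is kept. At most, add to 6.1.1 that the 6.1.4 stay also applies, whichever is longer, and that the stay runs to the end of the cycle if the dose of first toxicity is not reached again. This makes explicit what 6.1.1 already implies. If a reduced dose is kept from early in a cycle, the stay could be long (up to 28 − k days), and the sponsor should confirm that this is intended.

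All three are amendment wording only.

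### Table 2's dagger footnote permits re-challenge after toxicity at 9 mcg/day with no neurotoxicity exception, while its own row and section 6.1.1 require permanent discontinuation

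*Combined protocol and SAP*

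**What the plan says.** **Grade 3 neurotoxicity at 9 mcg/day.** Table 2 (section 6.1), neurological grade 3 row: "If the toxicity occurred at 9 mcg/day, or if the toxicity takes more than 7 days to resolve, discontinue blinatumomab permanently". Earlier in the same cell comes the restart instruction, "mild) and, then restart blinatumomab at the next lowest dose level", followed directly by a dagger. The dagger footnote defines the next lowest dose and then adds: "If the toxicity occurred at 9mcg/day, re-challenge after resolution to grade 1 or less may be attempted after appropriate pre-medication". A further sentence lets the investigator depart from the table after discussion with the PI.

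Section 6.1.1 covers "a grade 3 CNS event leading to treatment interruption at the dose of" 9 µg/day and states that it "will result in permanent treatment discontinuation".

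**CRS.** Section 6.1.2 allows resumption at 9 mcg/day on condition that "no neurological toxicity of greater than or equal to grade 3 occurred". The CRS grade 3 row of Table 2 reads "restart blinatumomab at the next lowest dose* after dexamethasone pre-medication (see table 1"; its asterisk leads to a note about seizures.

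**Other grade 3 events.** The row ends: "toxicity occurred at 9 mcg/day If the toxicity takes more than 14 days to resolve, discontinue blinatumomab permanently". Section 6.1.3 lets such events restart after resolution and names no dose exception.

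**Timing (secondary).** Section 4.0 sets 8-week cycles. Section 4.3 starts blinatumomab on day 15 of cycle 1 and day 1 of cycle 2, with two weeks off between courses. Footnote 3 of Table 4 (section 9.0) starts cycle 2 four to eight weeks after cycle 1 is completed. It places each response assessment two to four weeks after its cycle, and then also on day 57 plus or minus one week.

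**The concern.** A stop-or-restart rule for a severe neurological event should have one answer. Here a clinician who follows the dagger from the neurotoxicity row arrives at permission to restart, at the dose where that row orders a permanent stop. The permissive sentence sits under the table that staff would consult when the event happens. At stake is possible re-exposure of a patient whom the rest of section 6.1 would take off the drug.

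The timing point is smaller. The planned date of cycle 2, and so the calendar date of the second assessment, depends on which sentence is followed.

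**Working it through.** **1. The texts side by side, for an event at 9 mcg/day**

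| Place | Event | Instruction |
|---|---|---|
| Table 2, neurological grade 3 row | Grade 3 neurotoxicity | Stop permanently |
| Section 6.1.1 | Grade 3 CNS event | Stop permanently |
| Section 6.1.2 | CRS | Resume at 9 mcg/day only without grade 3 or higher neurotoxicity |
| Table 2, dagger footnote | Any toxicity reached by the dagger, including the neurological row | Re-challenge may be attempted |

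Two texts order a stop and a third is consistent with it. The footnote stands alone.

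**2. Does another clause settle it?** No order of precedence is stated. The PI-discretion sentence covers modifications other than those in the table, so it does not choose between two instructions that the table and its footnote both contain. The re-challenge sentence does not itself call for PI discussion.

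**3. Markers.** The CRS grade 3 row also sends the reader to the next lowest dose, but by an asterisk to the seizure note rather than by the dagger to the definition. In the 'Other' row the dagger does reach that definition.

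**4. The 'Other' grade 3 row.** Two conditions stand together with no joining word. By analogy with the neurological row, the missing text would make 9 mcg/day a reason to stop. By section 6.1.3 and the footnote, restart would be allowed. The clause straddles a break in the extracted table, so text may have been lost there. The documents do not decide the intent.

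**5. Can the affected number be sized?**
- Planned exposure at 9 mcg/day is cycle 1 days 15-21 (section 4.3), that is 7 of 28 + 28 = 56 infusion days, or 12.5%.
- Section 5.1.3 says neurologic events are most frequent in the first few days and on dose escalation. Escalation is by definition above 9 mcg/day.
- Section 5.1.2.7 gives a median onset of 9 days. Infusion day 9 is cycle 1 day 15 + 9 - 1 = 23, when the planned dose is 28 mcg/day. No split by grade or dose is given.
- Section 5.1.3 reports grade 3 neurotoxicity in 6 of 21 DLBCL patients: 6/21 = 28.6% (printed as 26%). That covers all dose levels.

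The share arising at 9 mcg/day is not given, so no number follows.

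**6. Cycle 2 start.** Convention: k weeks after a period ending on day d is day d + 7k + 1. The first infusion ends on day 15 + 28 - 1 = 42.
- Plan (sections 4.0 and 4.3): 42 + 14 + 1 = 57. This reproduces the stated two-week gap (days 43-56).
- Footnote 3, counted from day 42: 42 + 28 + 1 = 71 to 42 + 56 + 1 = 99, which is 2-6 weeks after day 57.
- Footnote 3, counted from day 56: 56 + 28 + 1 = 85 to 56 + 56 + 1 = 113, which is 4-8 weeks after day 57.

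Neither count gives day 57.

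**7. Assessment windows (day within cycle)**

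| Rule | Cycle 1 | Cycle 2 |
|---|---|---|
| Day 57 ± 7 | 50-64 | 50-64 |
| Section 4.4 | 50-64 (2 ± 1 weeks after day 42) | 50-64 (4 ± 1 weeks after day 28)* |
| Footnote 3, 2-4 weeks after infusion end | 57-71 | 43-57 |
| Footnote 3, 2-4 weeks after day 56 | 71-85 | 71-85 |

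*Only if section 4.4's consolidation cycle means the second blinatumomab cycle. Table 4 uses the word consolidation for ibrutinib plus nivolumab.

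**8. Statistical design.** With the beta(0.8, 1.2) prior and the rule P(rate > 0.4) > 0.8, the printed toxicity boundaries reproduce exactly: 4/6, 5/9, 7/12, 8/15 and 10/18.

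**The case against.** The strongest reply is that the stop rule already dominates. It is in the row itself, is repeated in section 6.1.1 and is respected in section 6.1.2. The dagger is attached to the phrase on the next lowest dose, serves the 'Other' row as well, and never names neurotoxicity. A specific rule normally overrides a general note. That is the sensible reading and probably the intended one, but the protocol does not say so and the dagger is printed in the neurological row.

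The safeguards also carry weight:
- Table 1 requires the PI to be notified of CNS events of grade 2 or higher.
- The planned 9 mcg/day week lies wholly within the day 15-31 admission.
- Section 6.1.4 puts restarts in hospital.
- Section 6.1.1 recommends MRI before resumption after a grade 3 event, although omitting it is not a deviation.
- Section 6.1.4 ends blinatumomab permanently if grade 3 or higher related toxicity recurs.

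These bound the harm from a wrong restart. They do not reconcile the texts.

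On timing, footnote 3 says that delays are expected, and the first assessment may run to day 64, so a start after day 57 can be legitimate. That does not explain a planned interval of four to eight weeks. It is fair to add that the largest gaps require counting from day 56; counted from the end of infusion, the assessment windows overlap in part.

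**Conclusion.** The contradiction is real and should be corrected: for grade 3 neurotoxicity at 9 mcg/day, the footnote permits what the row and section 6.1.1 forbid. The conclusion rests on the current text alone. The cycle 2 timing conflict is also real but secondary.

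Four stronger readings are not supported:
- **About 6 of 21 patients are affected.** A reader might infer this from the 6/21 rate. That rate covers all dose levels, and the 9-day median onset points away from the 9 mcg/day week.
- **Other grade 3 events at 9 mcg/day should be open to re-challenge.** The broken clause is equally compatible with a stop.
- **The safety stopping rule is compromised.** Under section 14.0, a grade 3 neurotoxicity that resolves within a week counts only if it recurs at grade 3 or higher on re-challenge, so one patient's classification could depend on which instruction is followed. The boundaries themselves are unchanged.
- **The primary endpoint is affected.** It remains response after two courses; only calendar dates move.

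**What to change.** **Main.** Add to the dagger footnote: *This does not apply to grade 3 neurotoxicity: if it occurred at 9 mcg/day, discontinue blinatumomab permanently. For CRS at 9 mcg/day, follow section 6.1.2.* In the CRS grade 3 row, change the asterisk to the dagger.

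**Question for the sponsor.** Which outcome was meant for 'Other' grade 3 events at 9 mcg/day? Once answered, align the row, the footnote and section 6.1.3.

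**Secondary.** In footnote 3 of Table 4, state that cycle 2 is planned for day 57, after the first response assessment, and that a later start is allowed for toxicity or a late assessment. Delete the two sentences that set a window of two to four weeks and keep only the day 57 (± 1 week) rule.

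**Cost.** Protocol wording only, suitable for the next amendment. Nothing changes in the endpoint definition, sample size, stopping boundaries or data collection.
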